10.7 Trial supervision

As the trial is a small pilot study of only 60 subjects in two centres both very experienced in perfusing donor livers *ex situ*, external supervision of the study processes is not considered necessary.

Because the treatment intervention is novel an internet meeting (e.g. Zoom or Teams) will be held between sites to review each of the first 4 cases, then the next 6, and then the last 10.

11 Assessment of Safety

Contact with the Medicines and Healthcare products Regulatory Agency (MHRA) has been made. They stated that “requirement for MHRA notification would depend on the manufacturer’s intended use of the device”. This trial will use the machine for the manufacturer’s intended use, and indeed it is trying to enhance its efficacy. They are content that this is not a clinical trial of a medicinal product (CTIMP).

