4.9 Trial objective and purpose

4.9.1 Primary objective

To evaluate the safety and feasibility of thrombolytic therapy delivered *ex situ*, viz:

- Is it possible to safely treat livers on the perfusion machine with a clot busting regimen?
- Is it associated with excess bleeding in the recipients?

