5.8.3 Trial

The trial will end if:

- 30 DBD and 30 DCD livers have been transplanted
- Evidence of residual thrombolytic activity in the livers post transplant. However, it is common in DCD liver transplantation for the patient to become coagulopathic post implant with evidence of fibrinolysis
- ≥ 5 cases of anastomotic or non-anastomotic strictures within six months of transplant

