11.3 Expected Serious Adverse Events

Liver transplantation is a life-saving procedure but is associated with serious life-threatening complications. It is expected that many of these will be encountered during the study and which we do not propose to report as AEs or SUSARs to the REC/Sponsors.

- Peri-operative death (within 48h) ~ 1 to 2%
- Death from graft failure or sepsis or other complication in the first year: 5%
- Primary non function: 4% for DCD livers; 1% for DBD livers
- Early allograft dysfunction (Olthoff criteria): 40% DCD, 25% DBD.
- Hepatic artery thrombosis: 4-15%, depending whether anomalous arterial supply required reconstruction or not
- Post reperfusion syndrome: 30%
- Biliary anastomotic breakdown 5%
- Post-operative haemorrhage requiring reoperation: 10%
- Acute rejection: 20%
- Acute kidney injury (Rifle definition): 50% DCD, 35% DBD.
- Chest complications: sepsis; effusion; paralysed right hemidiaphragm: common
- Ascites: universal if pre-existing ascites, common if not pre-existing.

- Complication associated with operative techniques in particular, or surgery in general (e.g. adhesions, adhesive obstruction, wound infection, wound hernia, wound dehiscence)
- Line sepsis
- Biliary anastomotic stricture: 20% DCD, 15% DBD
- Non-anastomotic strictures: 20% DCD, 8% DBD
- Retransplantation in first year: 17% DCD, 11% DBD.

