11.4.2 Assessment of causality

- Probable: A causal relationship is clinically / biologically highly plausible and there is a plausible time sequence between onset of the AE and administration of the investigational medicinal product and there is a reasonable response on withdrawal.
- Possible: A causal relationship is clinically / biologically plausible and there is a plausible time sequence between onset of the AE and administration of the investigational medicinal product.
- Unlikely: A causal relation is improbable and another documented cause of the AE is most plausible.
- Unrelated: A causal relationship can be definitely excluded and another documented cause of the AE is most plausible.

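### Oversight of bleeding does not fit the trial: scheduled reviews cover 20 of 60 cases, re-operation for haemorrhage is on the non-reported list, and no trial-ending criterion uses a bleeding event or amount

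*Protocol*

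**What the plan says.** **Supervision.** Section 2.6 of the Protocol lists no committees. Section 10.7 explains why external oversight is thought unnecessary: "As the trial is a small pilot study of only 60 subjects in two centres both very experienced in perfusing donor livers". In its place it offers online meetings between sites "to review each of the first 4 cases, then the next 6, and then the last 10". Section 5.2 gives three centres, and section 10.2 gives 60 recipients, half from each donor type.

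**Groups.** Section 4.7 puts six transplanted livers in each of the initial groups, at least one of them a control. Section 7 allocates one liver in six to FFP without TPA. Section 4.7 bases the dose for the later groups on fibrinolysis, measured by perfusate D-dimer. It makes no bleeding result a condition for opening a group.

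**The safety question.** Section 4.9.1 asks: "Is it associated with excess bleeding in the recipients". Section 5.6 makes blood loss after reperfusion a primary endpoint, and return to theatre for bleeding within 24 hours a secondary one.

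**Reporting.** Section 11.3 lists transplant complications "which we do not propose to report as AEs or SUSARs to the REC/Sponsors". One entry is "Post-operative haemorrhage requiring reoperation: 10" per cent. Section 11.2 expects no adverse reactions in recipients. Section 11.6 requires expedited reporting of treatment-related reactions that are both unexpected and serious.

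**End of trial.** Section 5.8.3 gives three grounds: recruitment complete, evidence of residual thrombolytic activity, or five or more strictures. The second is followed by the remark that "it is common in DCD liver transplantation for the patient to become coagulopathic post implant with evidence of fibrinolysis".

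**Causality.** In section 11.4.2 the grade Probable requires, among other things, that "there is a reasonable response on withdrawal".

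**The concern.** Bleeding is the harm this pilot is meant to assess. Section 4.6 names it as the main risk of thrombolysis, and section 4.1 notes excess bleeding where TPA was put into the hepatic artery during implantation. With no committee, detecting an excess while the trial runs depends on the case reviews, on event reporting and on the trial-ending criteria.

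The case reviews are sized for a smaller trial. The reporting rule excludes the most recognisable serious bleeding event. The trial-ending criteria give a count for strictures but use no bleeding event or amount. An excess could therefore build up case by case, be recorded as endpoint data, and not be looked at as a whole until the final analysis.

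**Working it through.** **1. The plan's own size.** Sections 5.3 and 10.2 give 30 DCD and 30 DBD transplants from about 45 and 35 perfusions. With one third and 15% of livers failing viability, 30 / (1 − 1/3) = 45 and 30 / (1 − 0.15) = 35.3. The figures reproduce, so 60 is the intended number of transplants.

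**2. Review coverage.** 4 + 6 + 10 = 20, and 20/60 = 33%. The remainder is 60 − 20 = 40, or 67%. This does not depend on which cases are the last 10.

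**3. Reviews against group changes.** The Protocol does not say whether a meeting follows each case or each block, or whether the last 10 are cases 11–20 or 51–60. Nor does it say whether DCD and DBD livers pass through the groups together or separately. Assume groups of six throughout, so that changes fall at multiples of 6 (one sequence) or of 12 (two cohorts in parallel):

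| Reading of 10.7 | Changes reviewed, multiples of 6 | Changes reviewed, multiples of 12 |
|---|---|---|
| Meetings after cases 1, 2, 3, 4, 10, 20 | none | none |
| Meetings after cases 1, 2, 3, 4, 10, 60 | none | none |
| Each of cases 1–20 reviewed singly | 6, 12, 18 | 12 |
| Each of cases 1–10 and 51–60 reviewed singly | 6, 54 | none |

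No reading covers all changes, and the text makes no review a condition for opening a group.

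**4. Number of centres.** Section 10.7 says two and section 5.2 says three. Section 10.2 expects 35–45 per site: (45 + 35) / 2 = 40 fits that range, while 80 / 3 = 26.7 does not. Section 5.4 also still reasons from a cohort of 20. That these sections were not updated is an inference, but the contradiction stands without it.

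**5. Events on the non-reported list.** At the 10% in section 11.3, 0.10 × 60 = 6 re-operations for haemorrhage are expected, of which 0.10 × 40 = 4 fall among cases with no scheduled review. If the rate were 20% in all recipients, these become 12 and 8. With 5:1 allocation, 60 × 5/6 = 50 receive TPA, with 5 events expected at 10% and 10 at 20%.

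**6. What one group can show.** With five treated livers, P(2 or more) = 1 − (1 − p)^5 − 5p(1 − p)^4:
- p = 0.10: 1 − 0.590 − 0.328 = 0.08
- p = 0.20: 1 − 0.328 − 0.410 = 0.26

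A single group separates the two rates poorly, and it has about one control. A review at a group change therefore needs cumulative data.

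**7. The reporting sections side by side.** Section 11.3 withholds re-operation for haemorrhage whatever its suspected cause or frequency. Under section 11.2 no reaction is expected, so a bleed attributed to TPA would be unexpected. If it is also serious under section 11.1.4, section 11.6 requires expedited reporting. The same event is thus both withheld and expedited. The sponsor's evaluation in section 11.4 depends on reports that section 11.3 holds back.

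**8. Causality wording (minor).** Section 6.3 says treatment is complete by the time of transplantation, so no recipient event can respond to withdrawal and none can be graded Probable.

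**The case against.** The case against a broader criticism is strong in several places.

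- A reader might infer that no trial-ending criterion concerns bleeding. The documents do not support that. Residual thrombolytic activity is the mechanism by which TPA would cause bleeding, and the sentence after it is a caveat that leaves the criterion vague without cancelling it. What stands is that no criterion uses a bleeding event or amount.
- A reader might infer that reviews stop at case 20 and miss every group change. That is one reading only. Case-by-case review, or a final block at cases 51–60, is also possible.
- A reader might infer continuing, unreviewed dose escalation. In the current version group C is cancelled and groups D and E use 10 mg in total. The only remaining increase is from A to B; later groups change infusion site or duration.
- A reader might infer that an excess of bleeding would meet no reporting duty. Sections 11.4, 11.5 and 11.6 leave some duty in place, and blood loss and return to theatre within 24 hours are collected. The defect is an unreconciled contradiction. Section 11.1.3 judges expectedness against product information, and section 4.6 calls bleeding the main risk, so a sponsor might class such a bleed as expected. That makes the conflict with section 11.2 sharper.
- No reporting duty depends on the grade Probable, and Possible remains available, so the causality wording carries little weight.
- Going without external supervision is openly justified for a small pilot, and a particular count-based pause rule would be a reviewer's preference.

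None of this touches the 20-of-60 coverage, the conflict over centres, or the placing of haemorrhage on the non-reported list.

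**Conclusion.** The concern holds in a limited form. The only stated inter-site oversight covers 20 of 60 cases, rests on a number of centres that section 5.2 contradicts, and is not linked to the opening of groups. Section 11.3 exempts re-operation for haemorrhage without exception, against the primary objective and sections 11.2 and 11.6. The one bleeding-related trial-ending criterion cannot be applied as written, having no assay or threshold.

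The coverage figure (40 of 60 cases, 67%, unreviewed) needs no assumption. The event counts assume the Protocol's 10% rate: 6 in 60 recipients and 4 in the 40 unreviewed. The 20% figures are illustrative. The comparison with group changes assumes groups of six throughout, which section 4.7 states only for the initial groups. The documents do not show that oversight would fail outright, only that these sections do not deliver what the bleeding objective needs.

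**What to change.** - **Section 10.7:** correct the number of centres and extend the inter-site reviews to all 60 cases. Hold one at the end of each group, before the next opens. Tabulate blood loss and re-operation for bleeding by TPA and FFP control, cumulatively as well as by group. State whether DCD and DBD livers move through the groups together.
- **Section 11.3:** take haemorrhage requiring re-operation off the non-reported list, so that it agrees with sections 11.2 and 11.6.
- **Section 5.8.3:** reconcile the trial-ending criteria with the bleeding objective, and say how residual thrombolytic activity is to be recognised given the caveat that follows it. Any threshold is for the sponsor to set.
- **Section 11.4.2 (minor):** remove or reword the withdrawal condition, which cannot be met for recipient events.

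The cost is a few more online meetings and reports for about 6 expected events in 60 recipients at the stated 10%. The endpoints in section 5.6 already call for the bleeding data, although re-operations after 24 hours would have to be captured as well.

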11.1 Definitions

The following definitions of adverse events and reactions apply to clinical trials of investigational medicinal products, **which this is not**; it has been modified accordingly. Nevertheless, we will use the terms adverse events/reaction for incidents explicable by the use of the TPA/FFP in this study.

11.1.1 Adverse event

Any untoward medical occurrence in a patient or clinical trial subject which does not necessarily have a causal relationship with this treatment. An adverse event would be any unfavorable and unintended sign (including an abnormal laboratory finding), symptom, or disease temporally associated with study treatment, whether or not considered related to the investigational medicinal product

11.1.2 Adverse reaction of an investigational medicinal product (AR)

All untoward and unintended responses to the treatment. All adverse events judged by either the reporting investigator or the sponsor as having a reasonable causal relationship to the treatment qualify as adverse reactions. The expression reasonable causal relationship means to convey in general that there is evidence or argument to suggest a causal relationship

11.1.3 Unexpected adverse reaction

An adverse reaction, the nature, or severity of which is not consistent with the applicable product information (e.g. investigator's brochure for an unapproved investigational product or summary of product characteristics (SmPC) for an authorised product). When the outcome of the adverse reaction is not consistent with the applicable product information this adverse reaction should be considered as unexpected.

The term “severe” is often used to describe the intensity (severity) of a specific event. This is not the same as “serious,” which is based on patient/event outcome or action criteria.

11.1.4 Serious adverse event or serious adverse reaction

Any untoward medical occurrence or effect that:

- results in death,
- is life-threatening
- requires hospitalisation or prolongation of existing inpatients' hospitalisation,
- results in persistent or significant disability or incapacity,
- is a congenital anomaly or birth defect.

Life-threatening in the definition of a serious adverse event or serious adverse reaction refers to an event in which the subject was at risk of death at the time of event; it does not refer to an event which hypothetically might have caused death if it were more severe.

11.2 Expected adverse drug reactions

No drug is being given to the recipient so no adverse reactions would be expected.

11.3 Expected Serious Adverse Events

Liver transplantation is a life-saving procedure but is associated with serious life-threatening complications. It is expected that many of these will be encountered during the study and which we do not propose to report as AEs or SUSARs to the REC/Sponsors.

- Peri-operative death (within 48h) ~ 1 to 2%
- Death from graft failure or sepsis or other complication in the first year: 5%
- Primary non function: 4% for DCD livers; 1% for DBD livers
- Early allograft dysfunction (Olthoff criteria): 40% DCD, 25% DBD.
- Hepatic artery thrombosis: 4-15%, depending whether anomalous arterial supply required reconstruction or not
- Post reperfusion syndrome: 30%
- Biliary anastomotic breakdown 5%
- Post-operative haemorrhage requiring reoperation: 10%
- Acute rejection: 20%
- Acute kidney injury (Rifle definition): 50% DCD, 35% DBD.
- Chest complications: sepsis; effusion; paralysed right hemidiaphragm: common
- Ascites: universal if pre-existing ascites, common if not pre-existing.

- Complication associated with operative techniques in particular, or surgery in general (e.g. adhesions, adhesive obstruction, wound infection, wound hernia, wound dehiscence)
- Line sepsis
- Biliary anastomotic stricture: 20% DCD, 15% DBD
- Non-anastomotic strictures: 20% DCD, 8% DBD
- Retransplantation in first year: 17% DCD, 11% DBD.

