4.6 Risks and benefits

The main risk of thrombolytic therapy is bleeding, but since this treatment will take place *ex situ*, and there will be a 60 minute washout period, there is likely to be little TPA left circulating. The plasma half-life of TPA *in vivo* is 4 to 5 minutes⁶. When the liver is removed from the perfusion machine it is flushed with 2 to 3 litres of preservation solution before being implanted, washing away any last traces of perfusate.

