11.6 Reporting of Suspected Unexpected Serious Adverse Reactions (SUSARs)

All suspected adverse reactions related to the treatment which occur in the concerned trial, and that are both unexpected and serious (SUSARs) are subject to expedited

reporting.

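### Section 11.3 exempts listed serious events from AE and SUSAR reporting by type, with no exception for events related to TPA/FFP, and the case review in 10.7 covers only 20 of 60 recipients

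*Protocol*

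**What the plan says.** Protocol 11.3 lists serious events that it expects to see after liver transplantation, "which we do not propose to report as AEs or SUSARs to the REC/Sponsors". The list includes "Post-operative haemorrhage requiring reoperation: 10" per cent, "Retransplantation in first year: 17% DCD, 11% DBD" and "Primary non function: 4% for DCD livers; 1% for DBD livers", with peri-operative death at 1 to 2% and first-year death at 5%.

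The neighbouring sections say:
- 11.1: "we will use the terms adverse events/reaction for incidents explicable by the use of the TPA/FFP in this study".
- 11.1.3: a reaction is unexpected if its nature or severity does not match the product information.
- 11.2: "No drug is being given to the recipient so no adverse reactions would be expected".
- 11.4: the investigator evaluates each adverse event and passes it to the sponsor where indicated. Causality is graded probable, possible, unlikely or unrelated (11.4.2).
- 11.5: the sponsor must promptly notify investigators, the ethics committee and the authority of findings that bear on subjects' health.
- 11.6: "All suspected adverse reactions related to the treatment which occur in the concerned trial" must be expedited if they are both unexpected and serious.

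On risk, 4.6 states: "The main risk of thrombolytic therapy is bleeding". It then argues that treatment outside the body and a washout period leave little active drug.

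On oversight, 2.6 lists no committees and 10.7 considers external supervision unnecessary. Section 10.7 instead plans inter-site meetings on the first 4 cases, the next 6 and the last 10, and it describes two centres. Section 5.2 gives three centres. Section 5.8.3 ends the trial early on a count of strictures or on evidence of residual thrombolytic activity after transplant.

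**The concern.** The exemption is defined by the kind of event and does not depend on cause. A SUSAR is by definition suspected to be related to treatment, and 11.1 ties the adverse event and reaction terms to incidents that TPA/FFP could explain. Saying that a listed event will be reported under neither term can therefore be taken to include a listed event that the investigator does think is related. Section 11.6 would send that event out within days if it is also unexpected. The protocol gives no order of precedence.

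Safety, including excess bleeding, is the primary objective (4.9.1), and 4.5 says that clinical use of TPA in an ex situ setting has not been reported. If 11.3 is followed literally, a death, lost graft or bleed attributed to the treatment would not reach the sponsor or the ethics committee through the reporting route.

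A second and separate weakness is that the scheduled inter-site review does not fit the present trial. Most recipients fall outside it, so these events are not looked at together as they accumulate.

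**Working it through.** **1. The reporting rules side by side.** Take a listed serious event, such as primary non-function, that the investigator grades as possibly related to TPA/FFP.
- Under 11.1 it qualifies as an adverse reaction.
- Under 11.2 no reaction is expected in the recipient. If the product information does not cover the event either, 11.1.3 makes it unexpected.
- Under 11.6 it is then related, unexpected and serious, so it is expedited.
- Under 11.3 it is on the list, so it is not reported as an AE or a SUSAR.

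Two rules give opposite instructions for one event. They agree only if 11.3 is taken to mean events with a background cause, and 11.3 does not say that.

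**2. Bleeding.** The product information is not at hand. If it lists bleeding, a related bleed may count as expected under 11.1.3 and so fall outside 11.6. Section 11.2, or the severity of the bleed, could point the other way. If it is expected, 11.6 does not apply, 11.3 exempts it and 11.4 leaves referral to the investigator. A statement that 11.6 prevails would therefore not be enough to get related bleeds reported.

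**3. Coverage of the case review.** Inputs: 10.7 (4, 6 and 10 cases) and 10.2 (60 recipients, 30 DCD and 30 DBD).
- Named cases: 4 + 6 + 10 = 20.
- Not named: 60 − 20 = 40, and 40/60 = 67%.

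**4. How many listed events to expect.** Rates from 11.3, applied to 30 DCD + 30 DBD recipients:
- Bleeding needing reoperation: 60 × 0.10 = 6.0
- Retransplantation in the first year: 30 × 0.17 + 30 × 0.11 = 5.1 + 3.3 = 8.4
- Death in the first year: 60 × 0.05 = 3.0
- Primary non-function: 30 × 0.04 + 30 × 0.01 = 1.2 + 0.3 = 1.5
- Peri-operative death: 60 × 0.01 to 60 × 0.02 = 0.6 to 1.2

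If events spread evenly over cases, the 40 cases outside the schedule would hold 6.0 × 40/60 = 4.0 of the bleeds and 8.4 × 40/60 = 5.6 of the retransplantations.

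These counts include controls. Some use first-year rates, although the last planned assessment is at 6 months (9.5.4), and the categories overlap. They show how common the exempt events are. They do not estimate how many related events would be missed.

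**5. Why a cumulative count helps.** Assume that one recipient in six is a control (section 7), which leaves 50 on TPA. At 10%, 50 × 0.10 = 5.0 reoperations for bleeding are expected. If the rate doubled to 20% (an assumption), 10 would be expected. The exact binomial chance of 10 or more in 50 is 0.025 at 10% and 0.56 at 20%. Each bleed alone looks ordinary, and the excess shows only in the running total.

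**The case against.** The best defence is that 11.3 speaks of complications of transplantation and so covers background events only. With 11.1 reserving the reaction terms for what TPA/FFP could explain, 11.4 requiring a causality assessment and 11.6 catching related reactions, the sections can form a workable scheme. Saying that an event will not be reported as a SUSAR may simply mean that it is not one. This reading is possible, and it is why the point is a literal conflict left unresolved and no more. What it lacks is a phrase in 11.3 that limits the exemption to unrelated events.

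There are also safeguards. Post-reperfusion blood loss is a primary endpoint and return to theatre for bleeding within 24 hours a secondary one (5.6). Graft and patient survival are recorded at 6 months (9.5.4). Residual thrombolytic activity, the direct route to TPA bleeding, can end the trial (5.8.3), and 11.5 obliges the sponsor to pass on safety findings. All of this stands. But the endpoints serve the analysis, the residual-activity criterion carries no number, and 11.5 works only if the sponsor has been told. Leaving anticipated complications out of individual reporting is a reasonable choice in transplantation, provided that related events are excepted.

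A reader might infer more than the text supports:
- *That an excess which nobody attributes to TPA is lost through the 11.3/11.6 conflict.* It is not. Section 11.6 concerns related events only, so an unattributed excess lies outside it on any reading. That gap comes from the lack of a running review.
- *That every related bleed is a SUSAR.* Step 2 of the working shows why this cannot be settled from the protocol.
- *That the 40 cases go wholly unexamined.* The outcomes are collected for all. What is missing is a scheduled joint review during the trial.

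**Conclusion.** The point holds as a defect in a stated rule. Section 11.3 exempts serious events by type, makes no exception for those judged related to TPA/FFP, and on its literal reading contradicts 11.6. The protocol does not settle which prevails, and the treatment's own named hazard is among the exempt events. That the other reading is available lowers the weight but does not remove the ambiguity.

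The review schedule is a second, independent weakness: 20 of 60 cases named, 40 (67%) not, and two centres where there are now three. It appears to have been carried over from a smaller plan.

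The expected counts assume that the 11.3 rates hold and that events fall evenly across cases. The figure of 50 TPA recipients assumes one control in six throughout, and the doubled bleeding rate is an illustration only. The reporting conflict rests on the wording and needs none of these numbers. Both changes should be made. Neither calls for a numerical stopping trigger or for sponsor reports of every death and graft loss whatever the cause.

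**What to change.** 1. **Section 11.3.** Delete the reference to SUSARs and limit the exemption to events judged unrelated to TPA/FFP (unlikely or unrelated on the 11.4.2 scale). State that any listed serious event judged possibly or probably related is reported to the sponsor. This includes bleeding, whether or not the product information lists it. State that 11.6 governs expedited reporting.
2. **Section 10.7.** Correct the number of centres and extend the inter-site review to all 60 cases, for example after every 10. At each meeting, table the cumulative numbers of deaths, primary non-functions, graft losses or retransplantations, and reoperations for bleeding among TPA recipients beside the 11.3 rates.

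The first change adds only reports of events that an investigator already considers possibly or probably related, which should be few. The second adds about 40/10 = 4 short meetings. Both use outcomes that the sites already see or record and need only a protocol amendment.
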